6.3 STARTING DOSES AND SCHEDULE

6.3.1.1 Experimental Arm (PM01183): Arm A

- 3.2 mg/m^2 on Day 1 q3wk (three weeks = one treatment cycle)

Dose will be rounded to the first decimal.

6.3.1.2 *Control Arm (PLD and topotecan): Arm B*

- **PLD starting dose and schedule:**

50 mg/m² on Day 1 q4wk (four weeks = one treatment cycle).

Dose will be rounded to the first decimal.

Patients previously treated with PLD will be assigned to receive topotecan if they are randomized to the control arm.

- **Topotecan starting dose and schedule:**

- 1.50 mg/m² daily on Days 1-5 q3wk (three weeks = one treatment cycle) for patients with calculated CrCL \geq 60 ml/min.
- 1.25 mg/m² daily on Days 1-5 q3wk for patients with calculated CrCL between 40 and 59 ml/min.
- 0.75 mg/m² daily on Days 1-5 q3wk for patients with calculated CrCL between 30 and 39 ml/min.

Dose will be rounded to the first decimal.

Skipped doses of topotecan will not be replaced.

Patients previously treated with topotecan will be assigned to receive PLD if they are randomized to the control arm.

However, if the number of patients randomized to either PLD or topotecan reaches 60% of the total number of patients expected in the control arm (i.e. 126 patients), then the treatment of choice in the control arm will be restricted to the less frequent control drug until the end of accrual (see Section [5.6](#)).

The dose for all three agents (PM01183, PLD or topotecan) will be capped at a body surface area (BSA) of 2.0 m² in those patients who have a greater BSA. BSA will be calculated according to the standard nomogram used at each center.

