4.2 Secondary Objectives

To evaluate:

- Overall survival (OS).
- Antitumor activity.
- Safety profile.
- Patient-reported outcomes (PRO).
- To characterize the plasma pharmacokinetics (PK) of PM01183 using a sparse sampling scheme in the PM01183 treatment arm (Arm A).
- Subgroup analyses of the PM01183 arm vs. PLD or topotecan.

- To conduct an exploratory pharmacogenetic and pharmacogenomic (PGx) sub-study.

4.3 *Endpoints*

Primary endpoint:

- **Progression-free survival (PFS) by IRC** is defined as the time from the date of randomization to the date of documented progression per RECIST v.1.1 or death (regardless of the cause of death). If the patient receives further antitumor therapy or is lost to follow-up before PD, PFS will be censored at the date of last tumor assessment before the date of subsequent antitumor treatment.

Secondary endpoints:

- **Progression-free survival (PFS) per RECIST v.1.1 by Investigator's Assessment (IA).**
- **Overall survival (OS)** will be calculated from the date of randomization to the date of death (death event) or last contact (in this case, survival will be censored on that date).
- **Landmark analyses:**
 - **PFS at 6 and 12 months by IRC/IA** will be the Kaplan-Meier estimates of the probability of being free from progression (per RECIST v.1.1) and death at these time points.
 - **OS at 12 and 24 months** will be the Kaplan-Meier estimates of the probability of being alive at these time points.
- **Best antitumor response by IRC/IA** will be the best response obtained in any evaluation according to the RECIST v.1.1. before progressive disease. Irrespectively of treatment arm, radiological and clinical tumor assessment will be performed symmetrically at baseline and every eight weeks from randomization until evidence of PD. Patients who finish treatment without PD will continue with the tumor assessments every eight weeks (\pm two weeks) from randomization until PD, start of a new antitumor therapy, death or date of study termination (clinical cut-off), whichever occurs first.
- **Duration of response (DR) by IRC/IA** will be calculated from the date of first documentation of response per RECIST v.1.1 (complete or partial response, whichever comes first) to the date of documented PD or death. The censoring rules defined above for PFS will be used for duration of response.

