5 SAMPLE CONSIDERATIONS

5.1 Randomization and Stratification

Central randomization will be implemented in all patients who fulfill the eligibility criteria. Randomization of patients should occur as close in time as possible to the administration of the first dose of study drug. Patients will be assigned to each treatment arm (Arm A or Arm B) at a 1:1 ratio. If the patient had not previously received PLD or topotecan, the assigned treatment in case that the patient is randomized to the control arm (Arm B) will be based on the reported Investigator's preference with regard to each one of these two drugs. However, if the number of patients randomized to either PLD or topotecan reaches the 60% of the total number of patients expected in the control arm (i.e., 126 patients), then the treatment of choice in the control arm will be restricted to the less frequent control drug until the end of accrual. Stratification will be performed according to ECOG PS (0 *vs.* ≥ 1), prior platinum-free interval [PFI] (1-3 months *vs.* >3 months) and prior chemotherapy (1-2 *vs.* 3 lines).

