5.2 Sample Size

This phase III clinical trial is designed to determine a statistically significant difference in PFS by IRC between PM01183 and a control arm with PLD or topotecan in ovarian cancer patients with platinum-resistant disease.

Patients will be randomized to receive PM01183 given as 3.2 mg/m² (Arm A) or either topotecan or PLD (Arm B).

The prospective assumptions are a 30% reduction in the relative risk of progression or death (HR=0.7) to be achieved with the experimental arm (PM01183), at a one-sided 2.5% significance level with at least 90% power, following exponential distributions and fulfilling the proportional hazard assumption. Median PFS with control arm is expected to be around 3.5 months. It is forecasted that an observed HR of approximately 0.8 will have enough power to reject the null hypothesis (HR=1).

Approximately 420 patients with platinum resistant ovarian cancer will be necessary to stratify and randomize at a 1:1 ratio over 18 months (~23 patients/month). The required 332 PFS events are expected to occur around six months after randomization of the last patient. Therefore, the IDMC meeting after the IRC review to test PFS is expected to occur about one year after randomization of the last patient.

With the prospective assumptions above mentioned, about 175 PFS events are expected in the control arm and 157 in the PM01183 treatment arm.

The IDMC will review the results of the analyses. The IRC will determine the patient's best response and assign the date of objective response or progression/censoring according to the RECIST v.1.1.

5.2.1 *Futility Analysis*

A futility analysis will be performed when 210 patients are recruited (i.e., ~105 patients enrolled in each arm). The recruitment will not be put on hold.

In the futility analysis, the sponsor will make no claim of efficacy, consequently this futility analysis and the final analysis to reject the null hypothesis ($HR=1$) are planned; the significance level will be determined by the actual number of observed events by IR. To maintain scientific integrity, type II error will be controlled by a spending function defined by O'Brien-Fleming boundaries. Following the prospective assumptions, the interim analysis will occur at less than one year after start of recruitment. At this moment, with the available information collected after balancing efficacy and safety, the IDMC might recommend stopping the trial.

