Multivariate models (main effects or including interaction terms, if appropriate) will include all stratification factors and/or prognostic factors/covariates widely reported and recognized by the scientific community: treatment (PM01183 vs. control), ECOG PS (0 vs. ≥ 1 or coded as 0 vs. 1 vs. 2) prior platinum-free interval (1-3 months vs. >3 months or used as continuous variable), prior chemotherapy (1-2 vs. 3 lines or coded as 1 vs. 2 vs. 3), geographical area (USA vs. Europe vs. rest of the world), investigator's preference for the control arm (Topotecan vs. PLD), age, age at diagnosis, race (caucasian vs. other), histology type (serous/papillary vs. other), histology grade (poorly/undifferentiated vs. other), primary tumor site (ovarian vs. other), FIGO stage at diagnosis (metastatic/locally advanced [stage III] vs. other), FIGO stage at study entry (metastatic vs. locally advanced [stage III]/other), BRCA status (mutated vs. other), clinical/radiological signs of intestinal subocclusion at entry (yes vs. no), site of current disease: lung/liver (yes vs. no), liver metastases (yes vs. no), number of prior metastatic sites (≤ 2 vs. >2), body mass index (BMI), height, weight, body surface area (BSA), time from diagnosis to first infusion, prior cytoreduction (optimal vs. suboptimal vs. no surgery), prior radiotherapy (yes vs. no), platinum resistance (primary vs. secondary), clinically evidence of ascites at baseline (yes vs. no), time elapsed from last dose of last prior platinum-containing regimen to randomization, prior antiangiogenic treatment

with bevacizumab (yes vs. no), prior PARPi (yes vs. no), presence of any bulky (< 50 mm vs. \geq 50 mm) lesion at baseline, measurable disease (yes vs. no), sum of all target lesion diameters, baseline CA-125, albumin value at baseline, PFS prior line, response to last platinum therapy (yes vs. no) and baseline global QoL. In addition, continuous variables categorized as discrete variables will also be investigated in the continuum range and if the adjustment is better then the continuous variable will be selected in the model.

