All variables with a good percentage of valid cases (approximately \geq 90%) will be included in the multivariate analysis. Within the multivariate stepwise Logistic/Cox regression analysis, the chosen significance level for entering an explanatory variable into the model will be 0.05 (for all variables not in the model, the one with the smallest p-value will be entered if the p-value is less than or equal to the specified significance level). The significance level for removing an explanatory variable from the model will be 0.05 (for all variables in the model, the one with the largest p-value will be removed if the p-value exceeds the specified significance level). The parameter estimates, hazard ratios/odds ratios and p-values of the variables retained in the model will be presented.

Forest plots for PFS and OS summarizing main results, stratification and factors/covariates used in multivariate analyses will be plotted⁽²⁾.

Median follow-up (FU) time for PFS and OS will be calculated in the descriptive way, only taking into account the censored values and using the Kaplan-Meier method for reversing the censoring values as described by Parmar⁽³⁾.

Concordance between IRC and IA PFS assessments will be evaluated by means of Kaplan-Meier curves. Forest plots for response will also be performed adapting them to show relevant information (e.g. percentages will be shown instead of medians).

Sensitivity analyses for different PFS censoring will be performed. The following approaches will be calculated: 1) Date of progression based on scheduled time instead of recorded date (e.g. if progression occurs in the eleventh week and assessment would have to be done in the eighth week then the expected date is used instead of the actual date); 2) First date of progression combining IRC and IA assessments (e.g. the lowest date between IRC and IA is used); and 3) Date of progression moved to the prior tumor assessment date (e.g. if progression has not been documented in the second assessment and is documented in the third assessment then progression date is moved to the second assessment).

Proportional hazard assumption for PFS and OS will be checked by means of a Cox regression including treatment and its interaction with survival time⁽⁴⁾. In case of strong rejection of proportionality, then restricted mean survival estimates will also be calculated in addition to HR^(5,6).

Main summary of efficacy analyses

Endpoint	Population	Statistics

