8.9 Subgroup Analyses

Subgroup analyses implemented a posteriori based on clinically findings will have an exploratory nature.

Some exceptions are the upfront preplanned exploratory analyses, such as efficacy subgroup analyses based on comparison of PM01183 with PLD or topotecan, subgroup analyses for stratification factors, and the analysis of the subset of patients who received a platinum compound as first subsequent treatment.

Pre-specified safety subgroup analyses are: by age (<65 years-old vs. \geq 65 years-old), by race (white vs. other), by number of prior chemotherapy lines (1-2 vs. 3 lines) and by geographical area (USA vs. Europe vs. rest of the world).

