Reason	IRC				IA			
	PM01183		Control		PM01183		Control	
	N	%	N	%	N	%	N	%
Target lesion								
Non-target lesion								
Death due to malignant disease								
Other*								

(*)Please specify.

Table 11.3.1.44 Censoring reason by IRC/IA

Reason	IRC				IA			
	PM01183		Control		PM01183		Control	
	N	%	N	%	N	%	N	%
Free of progression last tumor assessment								
Subsequent therapy before documented progression								
Not treated								
Other*								

(*)Please specify.

Subgroup analyses

Forest plots summarizing main results, stratification factors and covariates for the comparison between PM01183 and PLD will be plotted.

- Figure 11.3.1.45 PFS by IRC (PM01183 vs PLD)
- Figure 11.3.1.46 PFS by IA (PM01183 vs PLD)
- Figure 11.3.1.47 OS (PM01183 vs PLD)
- Figure 11.3.1.48 RR by IRC (PM01183 vs PLD)
- Figure 11.3.1.49 RR by IA (PM01183 vs PLD)
- Figure 11.3.1.50 DR by IRC (PM01183 vs PLD)
- Figure 11.3.1.51 DR by IA (PM01183 vs PLD)
- Figure 11.3.1.52 CA125 by IRC (PM01183 vs PLD)

Forest plots summarizing main results, stratification factors and covariates for the comparison between PM01183 and Topotecan will be plotted.

- Figure 11.3.1.53 PFS by IRC (PM01183 vs Topotecan)
- Figure 11.3.1.54 PFS by IA (PM01183 vs Topotecan)
- Figure 11.3.1.55 OS (PM01183 vs Topotecan)
- Figure 11.3.1.56 RR by IRC (PM01183 vs Topotecan)
- Figure 11.3.1.57 RR by IA (PM01183 vs Topotecan)
- Figure 11.3.1.58 DR by IRC (PM01183 vs Topotecan)
- Figure 11.3.1.59 DR by IA (PM01183 vs Topotecan)
- Figure 11.3.1.60 CA125 by IRC (PM01183 vs Topotecan)

Forest plots summarizing main results, stratification factors and covariates for the comparison between PM01183 and Control arm selecting patients who received as first subsequent therapy a platinum line will be plotted.

- Figure 11.3.1.61 PFS by IRC (PM01183 vs Control)
- Figure 11.3.1.62 PFS by IA (PM01183 vs Control)
- Figure 11.3.1.63 OS (PM01183 vs Control)

- Figure 11.3.1.64 RR by IRC (PM01183 vs Control)
- Figure 11.3.1.65 RR by IA (PM01183 vs Control)
- Figure 11.3.1.66 DR by IRC (PM01183 vs Control)
- Figure 11.3.1.67 DR by IA (PM01183 vs Control)
- Figure 11.3.1.68 CA125 by IRC (PM01183 vs Control)

In the forest plots continuous variables not categorized in the definition will be coded into two categories taking as reference the median value, below or equal the median value and above the median value.

Characteristics of responders

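### The per-drug efficacy figures and PRO tables compare the whole PM01183 arm with controls given PLD alone or topotecan alone, so their top-line estimates are not randomised comparisons

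*SAP*

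**What the plan says.** **How the control drug is set.** Randomisation is 1:1 between Arm A and Arm B, stratified by ECOG PS, platinum-free interval and prior lines. The control drug is not a stratum.

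- Protocol 6.3.1.2: "Patients previously treated with PLD will be assigned to receive topotecan if they are randomized to the control arm", and the mirror rule applies after prior topotecan.
- For patients who have had neither drug, the investigator's stated preference decides.
- SAP 5.1: once either drug reaches 126 control patients, the choice is "restricted to the less frequent control drug until the end of accrual".

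**What is compared.** SAP 4.2 lists as a secondary objective "Subgroup analyses of the PM01183 arm vs. PLD or topotecan". SAP 11.3 turns this into sixteen forest plots: Figures 11.3.1.45-52 for PLD ("Forest plots summarizing main results, stratification factors and covariates for the comparison between PM01183 and PLD will be plotted") and 11.3.1.53-60 for topotecan. Tables 12.8.2-12.8.4 repeat the PRO t-tests, responder percentages and mixed model with the control group redefined as PLD only, then topotecan only.

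**Which patients enter.** SAP 11.3 applies the ITT population, which SAP 3.1 defines by allocation. SAP 12 applies the safety population of SAP 3.2. Neither per-drug set restricts the PM01183 side. The next set in SAP 11.3 (Figures 11.3.1.61-68) does state a restriction, to patients whose first later therapy was platinum.

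**Status.** SAP 8.9: "Some exceptions are the upfront preplanned exploratory analyses, such as efficacy subgroup analyses based on comparison of PM01183 with PLD or topotecan".

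**The concern.** The PM01183 arm holds both kinds of patient: those who would have received PLD and those who would have received topotecan had they been allocated to Arm B. A PLD-only or topotecan-only control group holds one kind. Setting the whole arm against one control drug therefore mixes the treatment contrast with any prognostic difference between the two kinds of patient.

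A difference is plausible, since designation depends on earlier drugs and on clinical judgement, but no document shows one. If it exists, one comparison is biased towards PM01183 and the other against it. A reader could then conclude that PM01183 does better against one control drug than the other when it does not.

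**Working it through.** **1. The plan's own figure.** SAP 5.2: "The required 332 PFS events are expected to occur around six months after randomization of the last patient". Schoenfeld's formula with HR 0.70, one-sided 2.5%, 90% power and 1:1 allocation gives 4 × (1.96 + 1.2816)² / (ln 0.70)² = 330.4, so 331 events; the SAP has 332. At 332 events power is 90.1% and the critical HR is 0.806, matching the SAP's approximate 0.8. The documents give no event count or power for the per-drug comparisons.

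**2. Size of the per-drug control groups.** The cap is 60% of 210 = 126, so at full accrual each drug has between 84 and 126 control patients.

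**3. Bias in the efficacy top line.** Let g be the PFS hazard of topotecan-designated relative to PLD-designated patients. No document gives g; it is an assumption. With a 60/40 PLD/topotecan split and no treatment effect, a first approximation to the whole-arm log HR is:

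- versus topotecan: −0.6 × ln g
- versus PLD: +0.4 × ln g

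For g = 1.5 this gives exp(−0.6 × 0.405) = 0.78 and exp(0.4 × 0.405) = 1.18. For g = 0.67 it gives 1.27 and 0.85.

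Simulation used 210 per arm, uniform accrual over 18 months, exponential PFS with median 3.5 months in PLD-designated patients, no dropout and a Cox model. Data were cut at the 332nd event, except the g = 0.8 row, which used six months' follow-up after accrual. Repeat runs agree to about 0.01.

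| g | Whole arm vs topotecan | Whole arm vs PLD | Matched on designated drug |
|---|---|---|---|
| 0.67 | 1.27 | 0.85 | about 1.00 |
| 0.8 | 1.14 | 0.91 | about 1.00 |
| 1.0 | 1.00 | 1.00 | about 1.00 |
| 1.2 | 0.90 | 1.07 | about 1.00 |
| 1.5 | 0.77 | 1.16 | about 1.00 |

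At a 50/50 split and g = 1.5 the whole-arm HRs are 0.81 versus topotecan and 1.21 versus PLD. At 40/60 PLD/topotecan they are 0.84 and 1.26. The smaller control group takes the larger bias.

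**4. PRO.** If mean change scores differ by d SD between the designated groups (again an assumption), the whole-arm difference is biased by 0.6d versus topotecan and 0.4d versus PLD, in opposite directions. At d = 0.2 this is 0.12 and 0.08 SD. The standard errors are √(1/210 + 1/84) = 0.129 and √(1/210 + 1/126) = 0.113 SD. The two-sided 5% tests would then reject in about 15% and 11% of trials with complete data, and about 10% and 8% if half the patients contribute.

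**5. Precision after matching.** At 332 events the simulated standard error of the log HR rises from 0.146 to 0.175 versus topotecan (0.175/0.146 = 1.20) and from 0.127 to 0.143 versus PLD (0.143/0.127 = 1.13). Power at HR 0.70 falls from 71% to 54% and from 80% to 71%.

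Response, duration of response and CA-125 were not simulated.

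**The case against.** **The analysis set is specified.** A reader might infer that the SAP leaves the PM01183 comparator undefined. The documents do not support that. The ITT rule in SAP 3.1 and 11.3, the reference to the PM01183 arm in SAP 4.2, and the safety-population rule for SAP 12 together point to the whole arm. The point is therefore about a choice made, not an omission.

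**The efficacy figures largely contain the remedy.** They are to show covariates, and SAP 6.2 lists investigator preference as one. Each per-drug figure should therefore carry a preference row close to the matched estimate, differing only where prior therapy or the cap overrode preference. This stands: for efficacy, the problem is confined to the top-line row.

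**These outputs are exploratory.** That holds for the efficacy figures, and SAP 11.3 names no test for them, so a false-positive rate there would describe a decision the plan does not make. The SAP 8.9 label names efficacy analyses only as an example, so it does not clearly exclude PRO either.

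**The PRO case is modest.** The t-tests are on change from baseline, so a baseline difference alone is not enough. They also cover 58 items at several visits without multiplicity control, so a rise from 5% to 8-15% on one test would seldom decide anything. This limits the weight of the point but does not remove it: the tables print p-values by control drug, and the mixed model contains only treatment, time and their interaction.

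**Conclusion.** The point holds as a minor one. The top-line estimates in Figures 11.3.1.45-60 and the per-drug parts of Tables 12.8.2-12.8.4 are not randomised comparisons. They are biased in opposite directions if, and only if, the designated control drug is prognostic.

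The HR ranges rest on an assumed gap of 0.67 to 1.5, meant as what remains after the stratification factors, and on a 60/40 split. The PRO figures rest on an assumed difference in change scores.

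Two stronger readings are not supported. One is that the plan favours PM01183 against topotecan: no document gives a direction, and below a gap of 1 the signs reverse. The other is that the main result is compromised: the primary ITT test of Arm A versus Arm B does not depend on which control drug was given.

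**What to change.** - **Derive the designated drug.** Before any by-arm analysis, derive for every patient in both arms the control drug she would have received. The inputs are prior agents and preference (Listing 13.1.3) and whether the cap restriction was in force at her randomisation. For the cap, use the date sites were informed, because the Protocol synopsis has the sponsor notify them and this may lag the 126th patient.
- **Match the comparison.** Make the top-line row of each per-drug efficacy figure, and each per-drug PRO comparison, PM01183 patients designated to that drug versus controls designated to that drug. Label any whole-arm version as non-randomised.
- **State what matching does not repair.** Duration of response is analysed in responders only, and PRO is collected on treatment with missing data left out. Both remain selected comparisons.
- **Annotate safety Tables 12.5.9-12.5.12** with the same non-randomised note.
- **Optional:** one treatment-by-designated-drug interaction test, reported as low-powered. Its standard error is √(0.175² + 0.143²) = 0.226, so power for a true HR ratio of 1.5 is Φ(0.405/0.226 − 1.96), about 43%.

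The cost is SAP wording, one derived variable from data already collected apart from the notification date, and the wider intervals shown above. Keeping the whole arm with designated drug forced into the model gives practically the same standard errors (0.175 and 0.142), so it recovers no precision.

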8.5 Subsequent Therapies

A table summarizing the subsequent therapies received after discontinuation will be shown. Special attention will be focused on patients receiving any platinum compound as first subsequent treatment, and analyses to test between treatment arms if potential platinum-free interval prolongation is associated with survival.

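### The arm comparison among patients whose next therapy was platinum is not a randomised comparison and can show a spurious effect in either direction

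*SAP*

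**What the plan says.** The Subgroup analyses part of SAP 11.3 plans forest plots for the "comparison between PM01183 and Control arm selecting patients who received as first subsequent therapy a platinum line". There are eight: PFS by IRC and by investigator (Figures 11.3.1.61 and 62), OS (63), response rate (64, 65), duration of response (66, 67) and CA-125 response (68). Each also shows stratification factors and covariates, with otherwise uncategorised continuous covariates cut at the median.

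SAP 8.9 lists "the analysis of the subset of patients who received a platinum compound as first subsequent treatment" among the exploratory analyses planned in advance, next to the stratification-factor subgroups. It does not say that this subset, unlike those, is formed after randomisation.

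SAP 8.5 gives special attention to patients whose first subsequent treatment is platinum and plans "analyses to test between treatment arms if potential platinum-free interval prolongation is associated with survival". It names no model, does not define the prolonged interval, and does not say how survival time before platinum is handled. The platinum-interval covariates in SAP 6.2 run only up to entry or randomisation.

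**The concern.** Membership of the subset is decided after randomisation. A patient enters only if she survived study treatment, was fit for more, and was judged worth re-treating with platinum. Protocol 1.1 links a platinum-free interval above six months to a higher chance of responding to further platinum and to better prognosis. Entry can therefore depend on how long study treatment held the disease. The trial is open label, so the next therapy is chosen with the arm known. Randomisation no longer makes the two groups comparable.

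At stake is the reading of a favourable or unfavourable subset plot as a treatment effect, for example as evidence that PM01183 restores platinum sensitivity or prolongs survival through later platinum, when it may only reflect who was selected.

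**Working it through.** **1. Timing of selection against outcome.**

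| Figures | Outcome | When it is settled | Relation to starting platinum |
|---|---|---|---|
| 61, 62 | PFS | Progression or death, or censored at the last assessment before new therapy (SAP 6.1) | Before |
| 64, 65 | Response | Assessed until progression or new therapy | Before |
| 66, 67 | Duration of response | Same censoring rules as PFS | Before |
| 68 | CA-125 response | Assessed until progression or new therapy | Before |
| 63 | OS | Death or last contact | After |

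For seven of the eight figures, selection follows the outcome. In Figures 61 and 62 death cannot be a PFS event: a patient who dies before any further therapy is excluded, and one given platinum before progression is censored. For OS the order is reversed. Platinum precedes death, and every member has guaranteed survival from randomisation to platinum start.

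**2. The plan's own figure.** SAP 5.2 assumes a PFS hazard ratio of 0.70 "at a one-sided 2.5% significance level with at least 90% power", with 332 events. Schoenfeld's formula gives 4 × (1.960 + 1.282)² / (ln 0.70)² = 42.0 / 0.1272 = 330.4, so 331. At 332 events power is 0.901 and the critical hazard ratio is exp(−1.96 × 2/√332) = 0.806. The primary design reproduces. The subset has no such basis. If 10% to 40% of the 420 patients entered it (assumed), with the same 332/420 event fraction, it would hold 33 to 133 events, with power of about 17% to 54% for a hazard ratio of 0.70.

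**3. Large-sample illustration with no treatment effect.** The documents give a control median PFS of 3.5 months and entry with a platinum-free interval of 1 to 6 months. The rest is assumed: exponential PFS and post-progression survival (median 7 months) sharing a log-normal frailty with SD 0.6, and a uniform prior interval. Platinum goes to half of those whose prior interval plus PFS exceeds a threshold and who live more than one month after progression. There are 200,000 patients per arm, analysed by one-covariate Cox models. The thresholds are modelling devices, not clinical rules.

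| Threshold, PM01183 vs control (months) | Subset PFS HR | Subset OS HR |
|---|---|---|
| 9 vs 6 | about 0.65 | about 0.77 |
| 7 vs 6 | about 0.86 | about 0.91 |
| 6 vs 9 | 1.55 | 1.31 |
| identical | 1.00 | 1.00 |

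The true values are 1.00 throughout. Repeated runs of the first row gave 0.63 to 0.65 and 0.76 to 0.79. In that row, 16% of PM01183 patients and 28% of controls enter the subset.

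**4. Trial-size illustration with no treatment effect.** 420 patients, 18 months' accrual, 24 months' follow-up, 4,000 runs, one-sided 0.025 log-rank test. Assumed: gamma frailty (variance 0.01 to 0.5) and median post-progression survival of 8 months. Selection is on PFS alone, and half of those above the threshold receive platinum.

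| PFS threshold, PM01183 vs control (months) | PFS HR (falsely favours PM01183) | OS HR (falsely favours PM01183) |
|---|---|---|
| 4 vs 2 | 0.70–0.73 (34–45%) | 0.80–0.85 (10–15%) |
| 6 vs 3 | 0.64 (50%) | 0.74 (20%) |
| 3 vs 3 | 1.00 (2–3%) | 0.99–1.00 (2–3%) |

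A graded rule, with a base platinum probability of 15% against 30% rising with PFS, gave PFS HR 0.80–0.86 and OS HR 0.82–0.89, with false results in 11–23% and 6–14% of runs. In all null runs the full ITT comparison stayed at 1.00 with 2–3% rejections.

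**5. A real effect with one common threshold.** Using the step 3 model with a PFS hazard ratio of 0.70 and 6 months in both arms, subset OS is about 0.89 against 0.87 in ITT, and subset PFS 0.77 against 0.75. At common thresholds of 9 to 12 months subset OS is 0.93 to 0.95. The shift is toward no effect. In a separate trial-size run with a PFS effect, no OS effect and one selection rule, subset OS was 0.97 with 2.8% rejections, close to nominal.

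**The case against.** The strongest defence is the status of the analysis. SAP 8.9 labels it exploratory, the main efficacy analyses including OS stay on the ITT population, and no decision rule or claim is attached to the subset. All of that stands and limits the seriousness of the point. A reader might infer that the trial's type I error is compromised; the documents do not support that.

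Three other stronger readings also fail.

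- A reader might infer that selection follows every outcome. It does not follow OS, which is the outcome SAP 8.5 asks about.
- A reader might infer that the plots will show a false effect. With no treatment effect and the same selection in both arms, they do not. A false effect there needs selection to differ by arm, and the documents give no platinum rule or arm-specific threshold.
- A reader might take Figures 61 to 68 to be the test promised in SAP 8.5. No section says so. The fair criticism of SAP 8.5 is that its method is unspecified.

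It can also be said that a large imbalance would be visible, since Table 12.7.1 reports subsequent platinum by arm. That helps only in part. The table sits in the safety section, which uses the safety population, and is not limited to first subsequent therapy. Similar counts would not show that similar patients were chosen.

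**Conclusion.** The point holds in a limited form. The eight comparisons are non-randomised, and following the plan as written can give a biased arm effect in either direction if the choice of platinum differs by arm. In the large-sample model the null hazard ratio moves from 1.00 to about 0.86 (PFS) and 0.91 (OS) with a one-month gap in threshold, and to about 0.65 and 0.77 with a three-month gap. These sizes rest on assumed thresholds, frailty and post-progression survival; they are illustrations, not predictions. With one common threshold and a true PFS hazard ratio of 0.70, the OS distortion is small at 6 months (0.02 on the hazard ratio) and 0.06 to 0.08 at 9 to 12 months, toward no effect. The primary analysis is untouched. The exploratory label does not repair the comparison, and listing it beside baseline subgroups lends it credibility that it lacks. It should be corrected before the data are analysed.

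**What to change.** - **SAP 11.3:** drop Figures 11.3.1.61, 62 and 64 to 68, or show them as descriptive summaries by arm with no between-arm hazard ratio or p-value. Treat Figure 11.3.1.63 the same way.
- **SAP 8.9:** state that this subset is defined after randomisation and supports no claim of treatment effect.
- **Added table:** report by arm, on the ITT denominator, the number receiving platinum as first subsequent therapy and, among recipients, the interval from last prior platinum to that platinum.
- **SAP 8.5:** define that interval and name a method that respects timing. This could be a time-dependent or landmark model in all randomised patients, or survival from platinum start with the interval as a covariate. Label it non-randomised: survival from platinum start still carries the same selection, so it should not be read as an arm comparison.

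The cost is SAP wording, one table and a little modelling. Agent and start date are already in Listing 13.1.46, and the last prior platinum dose is needed for an existing SAP 6.2 covariate. One exploratory between-arm comparison is given up.
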